9.2.2.2 Time Periods and Dates

The study period is determined by the launch date of linaclotide and subsequent uptake. The study period starts on the date of linaclotide commercialisation in each of the countries: in UK in May 2013, in Spain in September 2014, and in Sweden in February 2013.

The end of the study period is defined by the last day of patient records in the available data cut, currently planned for 31 December 2017, to allow for sufficient follow-up time (long-term use) to have

the opportunity to accrue a sizable number of subjects for descriptive purposes, and for subpopulations of interest (those with potential off-label use and potential for abuse/excessive use). Please refer to the Study Size and Data Analysis sections below.

[figure not shown]
Additionally, the database's lag time (for collected data to be available in each database, estimated as up to 8 months) needs to be factored in to determine when data will be available.

Index date (or cohort entry date) will be defined as date of the first prescription (UK) or dispensation of linaclotide (Spain and Sweden). Baseline period will be the ≥ 12 -month period before index date.

The follow-up period for each study subject will be the time from the index date to the earliest of the following dates (end of follow-up date; one day is the minimum follow-up; Figure 1):

- End of the study period for follow-up
- Disenrollment from the database (date of transfer out of the practice)
- Date of last data collection
- Death
- 1.5 times the number of days of linaclotide supply after the expiry of the last linaclotide prescription during the study period (for a total of 2.5 times the last prescription duration) plus one additional day when a potential discontinuation could be assessed (please refer to section 9.3.3 Linaclotide Treatment Outcomes below)

Figure 1. Study Periods Linaclotide DUS

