 - Bacterial/viral/parasite lab information, when available (positive versus negative or no information)

For prevalence of chronic comorbidities, prior diagnoses, or history of digestive surgery at index date, the patient's entire medical history will be explored.

9.3.3. *Linaclotide Treatment Outcomes*

Secondary outcomes of this study will be linaclotide treatment patterns. The linaclotide exposure information is characterised by the linaclotide days of supply. Days of supply will be ascertained from the prescription/dispensation information recorded in the databases and the recommended dose (one capsule of linaclotide 290 µg taken once per day) and calculated by dividing the quantity prescribed/dispensed by the daily dose. Days of supply of one prescription/dispensation are expected to be around 28 days since the 28-capsule pack will be the most widely used package size. If package size is unknown, then the median duration for patients with this information will be used (and if no median can be estimated then 28 days will be used).

Linaclotide prescription patterns of interest are:

- Discontinuation of linaclotide: defined as no prescription of linaclotide in the period of 1.5 times the number of days of supply of the last linaclotide prescription following its expiry date (Sikka et al., 2005; Peterson et al., 2007): for example, for a 28-day prescription, no new prescription in the 43 days after the expiry date of the prescription supply. The date of discontinuation is the day after the date of expiry of the last linaclotide prescription. Time to discontinuation (permanently during the study period or temporarily) is the interval between the date of the first linaclotide prescription and the date of discontinuation. Discontinuation

will be reported separately for those who permanently discontinue during the study period and for those who discontinue temporarily and subsequently restart on linaclotide (see below).

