9.6. Data Management

We will collect electronic primary care patient records from the CPRD in the UK and electronic records on inpatient and outpatient admissions and dispensation of drugs in Sweden from the NPR and PDR. Routine procedures will include checking electronic files, maintaining security and data confidentiality, following analysis plans, and performing quality-control checks of all programmes. In Spain, SIDIAP will be in charge of the data management.

Each database custodian will maintain any patient-identifying information securely on site according to internal standard operating procedures. [REDACTED] will maintain the data cuts according to internal procedures.

An [REDACTED] data analyst will write and review programs to implement the analyses outlined in the Data Analysis section below. The project team will review all data output, including SAS® code as needed. Changes and corrections to programs stemming from the review will be made as appropriate. All programs will be saved and the process documented. Security processes will be in place to ensure the safety of all systems and data. Every effort will be made to ensure that data are kept secure so that they cannot be accessed by anyone except select study staff.

Appropriate data storage and archiving procedures will be followed (i.e., storage on compact disk read-only memory [CD-ROM] or digital versatile disk [DVD]) with periodic backup of files to tape. Standard procedures will be in place at each research centre to restore files in the event of a hardware or software failure.

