9.9. Limitations of the Research Methods

Categorisation of patients with IBS into IBS-C, IBS-D, or IBS-M might be challenging. Differentiation between IBS-C and chronic constipation will also be challenging. As a consequence, some degree of misclassification is to be expected.

The use of over-the-counter medications for the treatment of IBS-C-related symptoms, constipation, and diarrhoea is acknowledged as another study limitation (Hungin, 2003). Over-the-counter medications will not be available in the UK or in Sweden. For Spain, we will include over-the-counter medications; however, we expect under-recording of these in the database.

The CPRD provides a large, diverse, and representative sample of UK people using primary care services, which allows for generalizability of the study findings to the broader UK population. The CPRD (and its predecessor General Practice Research Database [GPRD]) have been widely used for observational studies, with over 890 studies published to date in peer-reviewed journals. The SIDIAP database includes information for 90% of the population resident in Catalonia, a region in the north-east of Spain, and resembles the data collected by UK databases. One limitation is that date of prescription is available for only the first prescription and, thereafter, only approximate date of dispensation is available. For Sweden, the NPR and PDR cover the entire Swedish population and have been previously used in observational studies including drug utilisation ones. However, no primary care data will be available, so diagnoses will be those determined by a specialist, which are expected to be required for the variables of interest for this study. The PDR is not complete with regard to drugs used in nursing homes. According to the National Board of Health and Welfare, about 1% of people aged 65–79 years live in nursing homes, and about 20% of people aged 80 or more years live in nursing homes in Sweden [Socialstyrelsen]. This may be reflected in potential lower numbers of elderly patient using linaclotide identified in Sweden.

The validity of research findings based on CPRD data as well as the other databases depends on the quality and completeness of data recorded. We are only able to identify comorbidities for which the patient has consulted their GP. Referrals are not always uniformly coded and may appear as free-hand text or letters within the database.

Interval censoring might have an impact on the precision of the results.

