Administrative data from inpatient hospital admissions and outpatient visits; and 4. Medical data regarding main and up to 21 secondary diagnosis using the ICD-10 classification, external cause of injury and poisoning, and up to 30 surgical procedures from public and private service providers. A quality control check of the NPR is performed periodically, and in 2007 the main diagnosis was missing from 1.0% of records. At present, the NPR is updated once a year.

Proposed Data Source: The Prescribed Drug Registry

The Swedish Prescribed Drug Register (PDR) has been functioning since July 2005 and contains data on all prescriptions dispensed to the entire Swedish population. Data collection is administered by the National Corporation of Swedish Pharmacies, a state-owned company responsible for the provision of pharmaceutical services to the whole country. Information from all prescriptions dispensed is transferred monthly to the National Board of Health and Welfare, which is responsible for maintaining the PDR.

The register contains the following data on drugs prescribed and dispensed in ambulatory care: dispensed item (substance, brand name, formulation, and package); dispensed amount, dosage, expenditure, and reimbursement; age, sex, and unique identifier (personal registration number) of the patient; place of residence of the patient (county, municipality, and parish); date of prescribing and dispensing; the practice (primary health care centre or hospital clinic) that issued the prescription; and the prescriber's profession (e.g., general practitioner; specialist in internal medicine, psychiatry, or paediatrics). All drugs are classified according to the ATC classification system. The register does not include data on over-the-counter (OTC) medications or drugs administered in hospitals or complete data on drugs that are used in ambulatory care but are administered during day care at hospitals. The register is not complete with regard to drugs used in nursing homes.

Italy

In Italy, data sources have limited reference population size or limited availability of variables relevant for the proposed study. Additionally, linaclotide sales in Italy started in September 2014 hence the sample size contributed by Italy is relatively small.

Excluded Data Source (Potential alternative): Health Search/CSD Longitudinal Patient Database

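### In Sweden, unrecorded nursing-home dispensing or emigration can be counted as linaclotide discontinuation, and section 9.9 warns only of lower elderly counts

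*Protocol*

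**What the plan says.** Section 9.6 gives the Swedish data as "electronic records on inpatient and outpatient admissions and dispensation of drugs in Sweden from the NPR and PDR". Exposure therefore rests on dispensings in the Prescribed Drug Register (PDR); diagnoses come from the National Patient Register (NPR).

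Section 9.3.3 has discontinuation "defined as no prescription of linaclotide in the period of 1.5 times the number of days of supply of the last linaclotide prescription", counted from its expiry. It dates the event as follows: "The date of discontinuation is the day after the date of expiry of the last linaclotide prescription".

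On the register, section 9.9 says "The PDR is not complete with regard to drugs used in nursing homes", and Annex 3 part B repeats "The register is not complete with regard to drugs used in nursing homes". Section 9.9 adds the Swedish figures: "about 1% of people aged 65–79 years live in nursing homes, and about 20% of people aged 80 or more years live in nursing homes". It then draws one consequence: "This may be reflected in potential lower numbers of elderly patient using linaclotide identified in Sweden".

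Section 9.2.2.2 ends follow-up at the earliest of study end, disenrolment, last data collection, death, or the end of the grace period after the last supply. Disenrolment is worded as "Disenrollment from the database (date of transfer out of the practice", closing the bracket there.

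**The concern.** Discontinuation is defined by the absence of a record, so any loss of recording that outlasts the gap looks like stopping. Section 9.9 treats incomplete nursing-home capture as a problem of who enters the cohort. The same gap can act after entry, when a user moves into a home and later supplies are not recorded. None of the listed ends of follow-up covers that, and none covers emigration, because the NPR and PDR have no practice to transfer out of.

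Time to discontinuation is a secondary endpoint, analysed by country, and Sweden is the largest planned contributor. Section 8.2 asks for the characteristics of patients who discontinue. Section 9.7.2 plans Cox models with indication and other baseline variables, and age is a listed baseline variable. A loss of capture that rises steeply with age could appear there as an age effect. If users without IBS-C are older, it could also tilt the comparison by indication.

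**Working it through.** **1. The protocol's own yardstick.** Section 9.5 plans about 8,800 patients to detect a hazard ratio (HR) of 1.2 for a characteristic held by 10%, with 40% having the event, 90% power and two-sided alpha 5%.

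- Events = (1.960 + 1.282)² / [0.10 × 0.90 × (ln 1.2)²] = 3,513.
- Patients = 3,513 / 0.40 = 8,783, which agrees with 8,800.
- Sweden's planned share (Table 3): 4,584 / 9,665 = 47.4%, which agrees with the stated 47%.

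These figures are not in dispute. HR 1.2 serves below as a measure of what the plan treats as detectable.

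**2. How long a loss must last.** For a 28-day pack the gap is 1.5 × 28 = 42 days after expiry (the protocol's example says 43). The whole window from the last dispensing is 2.5 × 28 + 1 = 71 days. An unrecorded period that outlasts the gap is counted as discontinuation, dated to the day after expiry.

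**3. Which exits have a named source.**

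| Exit | Spain and UK | Sweden |
|---|---|---|
| Death | Death date listed for SIDIAP (section 4.7); mortality linkage for SIDIAP and, at least in part, CPRD (Annex 3 B) | Listed as an end of follow-up in 9.2.2.2, but no source named in 4.7, 9.6 or Annex 3 B |
| Leaving the database | Transfer out of the practice | No counterpart defined; emigration not mentioned |
| Nursing-home entry | Not raised in the protocol | Capture stated to be incomplete; no rule |

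**4. Size of the nursing-home part.** Inputs from the protocol: 40% yearly discontinuation (section 9.5), and nursing-home residence of 1% at 65–79 and 20% at 80 or more (section 9.9). Everything else is assumed:

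- entry to a home at 0.2–0.5% per year at 65–79 and 3–7% per year at 80 or more;
- 25–100% of entrants losing capture;
- 10–30% of users aged 65 or more being 80 or older;
- constant hazards.

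True hazard h = −ln(1 − 0.40) = 0.511 per year. Capture-loss hazard c = entry rate × share losing capture. Spurious HR, against users with the same true hazard and no loss, = (h + c)/h. False share of recorded discontinuations = c/(h + c). One-year recorded discontinuation = 1 − exp(−(h + c)).

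| Age | c per year | Spurious HR | False share | Recorded at one year (true 40%) |
|---|---|---|---|---|
| 65–79 | 0.0005–0.005 | 1.001–1.010 | 0.1–1.0% | 40.0–40.3% |
| 80+ | 0.0075–0.07 | 1.015–1.137 | 1.4–12.1% | 40.4–44.1% |
| All 65+ | 0.0012–0.0245 | 1.002–1.048 | 0.2–4.6% | 40.1–41.5% |

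The extremes for all 65+ are (0.9 × 0.002 + 0.1 × 0.03) × 0.25 = 0.0012 and (0.7 × 0.005 + 0.3 × 0.07) × 1 = 0.0245.

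**5. Break-even.** A spurious HR of 1.2 needs c = 0.2 × 0.511 = 0.102 per year, above every scenario in the table.

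Section 9.5 also expects about a third of patients to stop after one pack, so the true hazard is not constant. The results are orders of magnitude.

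**The case against.** The other side has several good points.

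- **Capture is not said to stop.** A reader might infer that dispensing records end on entry to a home. The protocol says only that the register is incomplete there, and section 4.7 puts its coverage of prescribed medicines dispensed from primary care and outpatient specialists close to 100%. The share lost is not given. This stands: false discontinuation can happen, but not for every entrant.
- **Death is already an end of follow-up.** A reader might infer that Swedish deaths are counted as stopping. Section 9.2.2.2 lists death without a country exception, and section 9.2.2.1 requires patients to be alive at index. Annex 3 B describes NPR content in broad groups, including patient data, so a missing death date is not proven. This stands: the gap is that no Swedish source is named. It does not remove the emigration gap or the ill-fitting disenrolment wording.
- **The 65+ subgroup is for baseline description.** Section 9.7.1 uses it only for that, and loss during follow-up cannot affect it. This stands. Age reaches the discontinuation analysis only as a characteristic or covariate, and the protocol commits to no particular age effect.
- **The size rests on assumptions.** This stands, and in both directions. Dividing the stated 20% prevalence by an assumed mean stay of 2–4 years gives entry of 0.20/0.80/4 = 6.25% to 0.20/0.80/2 = 12.5% per year. With total loss of capture the HR at 80+ would be 1.12 to 1.24. That larger figure is tempting, but it treats all residents as entering after 80 and all of them as losing capture. The protocol supports neither.
- **Disclosure.** Section 9.9 already reports the incompleteness with prevalences. What it leaves out is the effect on an endpoint, which is more than a matter of wording.

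**Conclusion.** The point holds in limited form. If the plan is followed as written, some Swedish users whose nursing-home supplies go unrecorded, or who emigrate while on treatment, will be counted as discontinuing. The protocol has no rule for either and does not state the consequence.

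The direction is towards more and earlier discontinuation. For nursing homes it is concentrated at age 80 or more, with a spurious HR of about 1.02 to 1.14 there and about 1.00 to 1.05 over all users aged 65 or more. Both ranges depend on the assumed entry rates and share losing capture. Nursing homes alone stay below the planned HR of 1.2 in that range. The number of users aged 80 or more is not given, so Sweden's 47% share of the cohort is not a measure of how many are affected.

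The contribution of death and emigration cannot be sized from the protocol, and it gives no basis for saying that emigration falls mainly on the elderly. The primary objectives are unaffected by this mechanism. It merits a cheap improvement to the secondary analysis.

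**What to change.** 1. In section 9.2.2.2, define the Swedish equivalent of disenrolment as emigration. Name the source of emigration and death dates, obtain both through the personal identifier that already links the registers, and censor on them.
2. Add a sensitivity analysis of Swedish time to discontinuation, and of the Swedish Cox model, that excludes users aged 80 or more or reports them separately. An alternative is to censor at supply expiry when no drug of any kind is dispensed afterwards, but only with a window longer than the usual dispensing interval of other long-term medicines. Over the 42-day gap of a 28-day pack, that rule would also censor true stoppers who take nothing else or collect other medicines less often.
3. In section 9.9, add that incomplete nursing-home capture can inflate discontinuation in the oldest Swedish users, besides lowering their number.

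The cost is two date fields in the linkage request, one extra run, a few sentences, and slightly less precision in the sensitivity analysis. Table 1 expects Swedish data to the end of 2017 in January 2018 (PDR) and August 2018 (NPR), so protocol version 4.2 of January 2017 leaves time to request the dates.

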9.10. Other Aspects

No further aspects to be considered.

10. PROTECTION OF HUMAN SUBJECTS

Institutional review board approval and/or any other required reviews of the study protocol by specific committees will be obtained in accordance with applicable national and local regulations.

The study will be conducted in accordance with the International Society for Pharmacoepidemiology's (ISPE) Guidelines for Good Pharmacoepidemiology Practices (2007), the European Network of Centres for Pharmacoepidemiology and Pharmacovigilance's (ENCePP) Guide on Methodological Standards in Pharmacoepidemiology (ENCePP, 2011a). The ENCePP Checklist for Study Protocols (ENCePP, 2011b) will be completed.

The study will be registered in the ENCePP Electronic Register of Studies (ENCePP, 2010) after regulatory endorsement of the protocol.

The study will comply with the definition of the non-interventional (observational) study provided in Article 2(c) of Directive 2001/20/European Commission and its refinement provided in Chapter I.7 Section 1 of Volume 9A of the Rules Governing Medicinal Products in the EU: Guidelines on

Pharmacovigilance for Medicinal Products for Human Use (European Commission, 2008), and referred to in the International Conference on Harmonisation (ICH) of Technical Requirements for Registration of Pharmaceuticals for Human Use's Pharmacovigilance Planning (ICH, 2004) and the Guideline on Good Pharmacovigilance Practices, Module VIII—Post-Authorisation Safety Studies (European Medicines Agency [EMA], 2012a).

11. MANAGEMENT AND REPORTING OF ADVERSE EVENTS (AE)/ADVERSE REACTIONS

For studies in which the research team uses only data from automated health care databases, the ISPE provides the following guidance:

'Aggregate analysis of database studies can identify an unexpected increase in risk associated with a particular exposure. Such studies may be reportable as study reports, but typically do not require reporting of individual cases. Moreover, access to automated databases does not confer a special obligation to assess and/or report any individual events contained in the databases. Formal studies conducted using these databases should adhere to these guidelines.' (ISPE, 2007, Section VI)

The EMA *Guideline on Good Pharmacovigilance Practices, Module VI*, provides the following guidance:

'For non-interventional study designs which are based on secondary use of data, such as studies based on medical chart reviews or electronic healthcare records, systematic reviews or meta-analyses, adverse reactions reporting is not required. Reports of adverse events/reactions should only be summarised in the study report, where applicable.' (EMA, 2012b, Section C.1.2.1)

The linaclotide DUS does not require adverse events (AEs) to be reported in an expedited manner to European authorities.

Procedures for the collection and reporting to Allergan of AEs/reactions identified during the study conduct will be agreed with Allergan and put in place, in accordance with the provisions of *Module VI, Management and Reporting of Adverse Reactions to Medicinal Products*, from the EMA.

12. PLANS FOR DISSEMINATING AND COMMUNICATING STUDY RESULTS

12.1. Regulatory Communication Plan

Study protocol, study status, and report(s) will be included in regulatory communications in line with the RMP, PSUR, and other regulatory milestones and requirements.

12.2. Publication and Communication Plan

Any publication resulting from the work outlined in this proposal will be discussed with Allergan. [REDACTED] will ensure Allergan has adequate time to review and comment on any manuscript or abstract developed. For all publications of [REDACTED] project work, [REDACTED] adheres to the authorship definitions and requirements as stated in the *Uniform Requirements for Manuscripts Submitted to Biomedical Journals* from the International Committee of Medical Journal Editors (ICMJE) 2013, repeated in part, as follows:

- Authorship credit should be based on: 1) substantial contributions to conception and design, or acquisition of data, or analysis and interpretation of data; 2) drafting the article or revising it critically for important intellectual content; and 3) final approval of the version to be published. Authors should meet conditions 1, 2 and 3
- All persons designated as authors should qualify for authorship and all those who qualify should be listed
- Each author should have participated sufficiently in the work to take public responsibility for appropriate portions of the content

- Acquisition of funding, collection of data, or general supervision of the research group, alone, does not justify authorship

Study results will be published following guidelines of the ICMJE (2010) and communication in appropriate scientific venues, e.g., ISPE will be considered. When reporting results of this study, the appropriate Strengthening the Reporting of Observational Studies in Epidemiology (STROBE) checklist will be followed (STROBE, 2007).

In its *Guidelines for Good Pharmacoepidemiology Practices*, ISPE contends that ‘*there is an ethical obligation to disseminate findings of potential scientific or public health importance*’ (ISPE, 2007, Section V). This would include results pertaining to the safety of a marketed medication. Study results will be published following guidelines, including those for authorship, established by the ICMJE (2010).

The marketing authorisation holder and the investigator have agreed on a publication policy allowing the principal investigator to prepare publications independently based on the study results, irrespective of data ownership. The marketing authorisation holder will be entitled to view the results and interpretations included in the manuscript, and provide comments prior to submission of the manuscript for publication (EMA, 2012a, Section VIII.B.7).

